7.11.2 Pharmacodynamic Analysis

During the clinical development of modakafusp alfa, a range of biomarkers will be assessed to test for their correlation with safety and efficacy. Markers that will be studied are markers linked to the drug itself, to the treated disease, or to patient factors.

A pharmacodynamic analysis will be included in CSR only if there is a trend.

7.11.3 Immunogenicity Analysis

The immunogenicity of modakafusp alfa will be assessed by determining anti-modakafusp alfa antibody (ADA) incidence and characteristics (eg, titer and specificity) and by determining neutralizing antibody (NAb) incidence. All ADA and NAb data will be listed. Percent of patients with positive ADA or NAb, percent of patients with positive ADA by domain specificity, and summary statistics of ADA titer at each timepoint will be summarized by dose schedules and dose levels by study phases. Percent of patients with positive ADA and NAb at baseline and positive ADA (final result and by domain specificity) and NAb at any post-baseline time point during the study will be summarized. Additional summary of the ADA kinetics including transient- vs. persistent-ADA, preexisting ADA, treatment-induced, or treatment-boosted ADA will be summarized, as applicable. ADA titer distribution over time will be presented through a box-plot on a logarithmic scale. The impact of ADA on the PK profile, drug efficacy, pharmacodynamic profile, and clinical safety will be evaluated and summarized, if possible. These analyses will be descriptive and exploratory in nature and may be included in CSR if there is a trend.

7.12 Safety Analysis

For Part 3 extension cohorts, analysis and review will assess the safety data across the treatment arms as well as in the patients with low body weight. Data to be reviewed will be summarized by treatment arm as well as by body weight (e.g., ≤ 80 kg and > 80 kg). With additional cumulative data, the weight subgroups may be further subdivided. The data might be included in the CSR if there is a safety trend identified in a specific low body weight group.

CONFIDENTIAL

7.12.1 Adverse Events

Adverse events will be coded using the Medical Dictionary for Regulatory Activities (MedDRA) Version 24.0 or later (based on version at time of database lock). Treatment-emergent is defined as any AE that occurs after administration of the first dose of any study treatment through 30 days after the last dose of any study treatment.

Treatment-emergent AEs will be summarized by MedDRA system organ class (SOC), and preferred term. For summary tabulations the following hematologic abnormalities coded to MedDRA preferred terms in the Investigations SOC will be pooled with the appropriate clinical terms in the Blood and lymphatic system disorders SOC:

MedDRA Preferred Term (Investigation SOC)	Mapped to (Blood and lymphatic system disorders SOC)
Neutrophil count decreased	Neutropenia
Platelet count decreased	Thrombocytopenia
Hemoglobin decreased	Anemia
White blood cell count decreased	Leukopenia

Treatment-emergent AEs will also be summarized by the National Cancer Institute Common Terminology Criteria for Adverse Events (NCI CTCAE) Version 5.0 or later.

Summary tabulations will include the following categories:

- Treatment-emergent AEs.
- Drug-related treatment-emergent AEs.
- Grade 3 and Grade 4 treatment-emergent AEs (based on maximum severity).
- The most commonly reported treatment-emergent AEs (i.e., those events reported by $\geq 10\%$ of all patients).
- Serious treatment-emergent adverse events (SAEs).
- Drug-related serious treatment-emergent adverse events.
- Grade 3 and Grade 4 treatment-emergent SAEs (based on maximum severity).
- Grade 3 and Grade 4 drug-related treatment-emergent SAEs (based on maximum severity).
- Grade 5 treatment-emergent AEs.
- Grade 5 drug-related treatment-emergent AEs.
- Treatment-emergent AEs resulting in discontinuation of study drug.
- Treatment-emergent AEs resulting in study drug modifications (including discontinuation, delay, reduction, and interruption).
- Treatment-emergent AEs resulting in dose delays.

- Treatment-emergent AEs resulting in dose reductions.
- Treatment-emergent AEs resulting in drug interruptions.
- Treatment-emergent AEs resulting in drug infusion interruptions.
- Treatment-emergent AESI – all Grades.
- Grade 3 or higher treatment-emergent AESI.
- Serious treatment-emergent AESIs
- Treatment-emergent haemorrhage standardised MedDRA query (SMQ) AEs
- Drug-related treatment-emergent haemorrhage SMQ AEs.
- Grade 3 and Grade 4 treatment-emergent haemorrhage SMQ AEs.
- Serious treatment-emergent haemorrhage SMQ AEs
- Grade 5 treatment-emergent haemorrhage SMQ AEs.

All summaries will be by dose schedule and dose levels by phases (escalation, expansion, and extension cohorts) for patients in the safety analysis set.

Patients with the same AE more than once will have that event counted only once within each SOC, and once within each preferred term. Patients with the same AE more than once will have only the maximum intensity of that event counted once within each SOC, and once within each preferred term.

Most commonly reported (at least 10% of all patients) treatment-emergent AEs will be presented by preferred term only. Patients with multiple occurrences of the same AE will have that event counted only once within each preferred term.

AE of special interest from a scientific and medical perspective (AESI) will be reported by preferred terms. In this study, infusion-related reactions (IRR) are considered as AESIs. The IRR signs and symptoms will be reported separately by preferred terms under the AESI tables only.

An overall summary treatment-emergent AE table will include numbers and percentages of patients who had any treatment-emergent AE, drug-related treatment-emergent AE, Grade 3 or higher treatment-emergent AE, grade 3 or higher drug-related treatment-emergent AE, serious treatment-emergent AE, drug-related serious treatment-emergent AE, serious treatment-emergent AE leading to study drug discontinuation, treatment-emergent AE resulting in study drug discontinuation, and on-study deaths. On-study death is defined as deaths that occur between the first dose of study drug and up to 30 days after the last dose of study drug and deaths that occur after 30 days after the last dose of study drug but are assessed as related to study drug.

A by-patient listing of DLTs as identified by the investigator that occur during Cycle 1 of treatment will be presented by dose schedule and dose levels for all patients enrolled during the dose escalation portion of this study. Patients will be grouped by the dose level to which they were originally assigned, including those who receive subsequent treatment at a lower or higher dose level. DLT-like events identified programmatically after Cycle 1 in Part 1 escalation cohorts and Part 2 expansion cohorts will be summarized and also be presented in a by-patient listing. Please refer to Appendix C for details.

A by-patient listing of all deaths regardless of whether on study or not will also be presented. In this listing, on-study deaths will be flagged.

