• To explore potential biomarkers to test their correlation with clinical efficacy and safety parameters.

Part 3 Extension:

- To explore predictive biomarkers of response and resistance.
- To characterize MRD negativity at a higher sensitivity in patients achieving CR.
- To evaluate generic health-related quality of life/health status as measured by the EuroQoL-5-Dimensions-5 Levels (EQ-5D-5L) instrument.

Subject Population: Subjects aged 18 years or older with relapsed/refractory MM.

Number of Patients	Number of Sites
Part 1 Escalation: 36 to 51 evaluable patients. Part 2 Expansion: Approximately 100 patients: 4 planned	Approximately 100 investigational centers globally.
expansion cohorts will each include a total of 25 patients. Part 3 Extension: Approximately 236 patients (~118 per	
arm). After global patient enrollment is completed in Part 3,	
enrollment will continue for the China continuation cohort until about 15% of the total sample size is reached at the	

selected dose (eg, 18 patients based on 118 patients	
treated at the selected dose[s]).	

Dose Levels

Phase 1 Dose Escalation: Modakafusp alfa infusions will be escalated as follows: 0.001, 0.01, 0.1, 0.75, 1.5, 3, 6, 9, and 14 mg/kg.

Evaluation of intermediate doses is permissible following discussions between the sponsor and the investigators.

Part 2 Expansion Cohorts with Dexamethasone:

Modakafusp alfa infusion at MTD/OBD as determined in the Part 1 dose escalation.

Dexamethasone 40 mg (20 mg if age >75 years).

Part 3 Extension: Modakafusp alfa 120 mg and 240 mg Q4W.

Route of Administration:

Modakafusp alfa: Intravenous (IV).

Dexamethasone: Oral (PO)

Duration of Treatment

Modakafusp alfa for up to 1 year (Parts 1 and 2); however, patients with clinical benefit can continue treatment beyond 1 year with explicit sponsor approval. Patients in Part 3 may continue treatment until disease progression. If the investigator considers that treatment after PD is in the patient's best interest, it can be approved after consultation with the sponsor.

Period of Evaluation

approximately 90 months.

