AE: adverse event; IRR: infusion-related reaction; TEAE: treatment-emergent adverse event. This table does not include guidance for the management of bleeding TEAEs, which is found in Table 8.e or for the management of IRRs, which is found in Table 8.g, Table 8.h, Section 8.7.1.1.1, and Section 8.7.1.1.2.

8.4.3.2 Part 3

Part 3 dose modification recommendations for hematologic and nonhematologic toxicities are detailed in Table 8.b and Table 8.c, respectively, and Part 3 dose reduction levels are found in Table 8.d.

Table 8.b Part 3 Dose Modification Recommendations for Modakafusp Alfa Hematological Toxicities

This table does not include guidance for management of bleeding TEAEs and IRRs. Refer to Table 8.e for the management of bleeding TEAEs and Table 8.g and Table 8.h for the management of IRRs.

Criteria	Action
Grade 1 and 2 AEs	No dose reductions or interruptions.
Grade 3 and 4 AEs	Hold modakafusp alfa next infusion until resolution to Grade ≤2 then resume treatment.
	Consider growth factors and/or transfusion according to local practice.
	If the next cycle of modakafusp alfa is delayed for >28 days, study treatment should be discontinued unless the investigator considers that the patient will receive benefit continuing in the study.
	Dose reduction can be considered.

AE: adverse event; IRR: infusion-related reaction; TEAE: treatment-emergent adverse event. This table does not include guidance for the management of bleeding TEAEs, which is found in Table 8.e or for the management of IRRs, which is found in Table 8.g, Table 8.h, Section 8.7.1.1.1, and Section 8.7.1.1.2.

Table 8.c Part 3 Dose Modification Recommendations for Modakafusp Alfa Non Hematological Toxicities

This table does not include guidance for management of bleeding TEAEs and IRRs. Refer to Table 8.e for the management of bleeding TEAEs and Table 8.g and Table 8.h for the management of IRRs.

Criteria	Action
Grade 1 and 2 AEs	No dose reductions or interruptions. Treat according to local practice.
Grade 3 AEs and Asymptomatic Grade 4 laboratory AEs	Hold modakafusp alfa next infusion until resolution to Grade ≤1 or baseline, and then resume treatment.
	1st occurrence: Resume treatment at either the same dose or reduced dose at the discretion of the investigator.
	Subsequent occurrence: Reduce modakafusp alfa by 1 dose level.

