8.4.4 Criteria for Discontinuing Modakafusp Alfa

Potential discontinuations of modakafusp alfa should be discussed with the sponsor or contract research organization (CRO) before implementation.

Modakafusp alfa should be discontinued in patients experiencing an AE in Cycle 1 meeting criteria for a DLT for which the investigator considers that retreatment of the patient could be dangerous.

If the next cycle of modakafusp alfa is delayed for >14 days (>28 days for Part 3) because of modakafusp alfa—related toxicities, study treatment should be discontinued unless the investigator considers that the patient will receive benefit continuing in the study. Patients will

be evaluated 30 days (EOT visit) after the last dose of modakafusp alfa or right before the start of subsequent systemic anticancer therapy to permit the detection of any delayed TEAEs.

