10.3 Monitoring of AEs and Period of Observation

AEs, both nonserious and serious, will be monitored throughout the study as follows:

• AEs will be reported from *the signing of informed consent* through 30 days after administration of the last dose of study drug or the start of subsequent anticancer therapy, whichever occurs first, and recorded in the eCRFs.

• SAEs:

- Serious pretreatment events will be reported to the Takeda Global Pharmacovigilance department or designee from the time of the signing of the ICF up to first dose of study drug and will also be recorded in the eCRF.
- Related and unrelated treatment-emergent SAEs will be reported to the Takeda Global Pharmacovigilance department or designee from the first dose of study drug through 30 days after administration of the last dose of study drug, even if the patient starts nonprotocol therapy, and recorded in the eCRF. After this period, only related SAEs must be reported to the Takeda Global Pharmacovigilance department or designee. SAEs should be monitored until they are resolved or are clearly determined to be caused by a patient's stable or chronic condition or intercurrent illness(es).

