- Patients who discontinue for reasons other than PD will continue PFS follow-up every 4 weeks from the EOT visit until the occurrence of PD, death, the start of subsequent systemic antineoplastic therapy, study termination, or until 6 months after the discontinuation of study treatment, whichever occurs first.
- End-of-treatment laboratory assessments are to be performed prior to the patient starting a new treatment or a maximum of 30 days following the last dose.
- aa. Schedule D Visits for C1D3 and C2D3 may be removed at a future time if no longer needed depending on MTD/OBD.
- bb. Dexamethasone will be added to the MTD/OBD of one or more schedule(s) as additional cohort(s). Dexamethasone will be given as a once weekly oral dose of 40 mg. Patients over 75 years of age will receive a reduced dose of dexamethasone (20 mg, same schedule) (refer to Section 8.1).
- Antiplatelet antibodies will be collected as indicated in the Schedule of Events until the sponsor communicates to the sites that a sufficient number of samples have been obtained to stop the collection.
- dd. Predose and at 4 hours (± 30 minutes) after the end of infusion.
- ec. Strongly recommended for >6 mg/kg dose group only.
- ff. Coagulation panel (prothrombin time/international normalized ratio, activated partial thromboplastin time, fibrinogen, D-Dimer) to be performed if clinically significant bleeding occurs.

Study Period	End of Treatment P, T	Disease Assessment	
Visit Name	30 (+10) days after last dose or the start of	(PFS Follow-Up) q	OS Follow-Up q
Window Allowed	subsequent systemic anticancer therapy, whichever occurs first	Every 4±1 week	Every 12 weeks ±1 week
ECOG performance status	X		
12-lead ECG ^c	X		
Physical examination ^b	X		
Vital signs ^d	X		
Monitoring of concomitant medication and procedures	Recorded from signing of the ICF through 30 (+10) days after last dose of study drug or start of subsequent systemic anticancer therapy, whichever occurs first.		
AE reporting	Recorded from signing of the ICF through 30 (+10) days after last dose of study drug or start of subsequent systemic anticancer therapy, whichever occurs first.		
	SAEs will be reported from signing of ICF through 30 (+10) days after last dose of study drug, even if the patient starts nonprotocol therapy.	Only study drug-related SAEs will be reported	
Imaging Assessments			
Skeletal survey e	(X)	(X)	
CT, PET-CT, or MRI scan e	(X)	(X)	
Laboratory Assessments			
Serum chemistry ^f	X		
Hematology ^g	X		

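### In patients who never resume after a hold, new adverse events starting on days 31 to 56 after the last Part 3 dose fall outside the treatment-emergent tables

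*SAP*

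**What the plan says.** - **Window.** SAP 7.12.1 counts as treatment-emergent "any AE that occurs after administration of the first dose of any study treatment through 30 days after the last dose of any study treatment". The tabulations listed there, including serious, Grade 5, leading to discontinuation and haemorrhage SMQ, are all of treatment-emergent events.
- **Dosing interval.** The Part 3 regimen in Protocol 2.0 is "Modakafusp alfa 120 mg and 240 mg Q4W".
- **Delay rule.** Table 8.b in Protocol 8.4.3 (Part 3 haematological toxicity) says: "If the next cycle of modakafusp alfa is delayed for >28 days, study treatment should be discontinued". Protocol 8.4.4 sets the general limit at "delayed for >14 days (>28 days for Part 3". The limit is not absolute: "study treatment should be discontinued unless the investigator considers that the patient will receive benefit continuing in the study".
- **Collection.** Protocol 10.3 records AEs to 30 days after the last dose, or to the start of subsequent anticancer therapy if that comes first, and reports all SAEs to 30 days. For SAEs it then says: "After this period, only related SAEs must be reported". Appendix A Table 11 (Parts 1 and 2) allows a little longer for AEs: "Recorded from signing of the ICF through 30 (+10) days after last dose of study drug".
- **Deaths.** The on-study deaths in the SAP 7.12.1 overall summary also include "deaths that occur after 30 days after the last dose of study drug but are assessed as related to study drug". All deaths are listed without a time limit, and the serious AE listing in SAP Appendix A is not restricted to treatment-emergent events.

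**The concern.** The window closes two days after the next Q4W infusion is due, but a patient can be held for four weeks beyond that date and still be a candidate for treatment. Whether an event during the hold is tabulated then depends on what happens later. If the patient is redosed, the last dose moves forward and the event is inside the window. If not, the earlier infusion becomes the last dose and the event is outside.

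For bleeding, the event itself can settle the matter. Table 8.e of the protocol calls for discontinuation at Grade 4 bleeding and at Grade 3 bleeding with Grade 4 thrombocytopenia. A bleed of that kind starting on day 40, during a hold for low platelets, makes the dose 40 days earlier the last one and so removes itself from the haemorrhage tables. A fatal bleed does the same.

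At stake is the completeness of the by-dose tables of serious, fatal and haemorrhagic events. Part 3 chooses between doses on risk-benefit, and Amendment 10 v2 was written to mitigate the risk of fatal haemorrhage after a SUSAR. If few such events occur, one missing event can matter.

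**Working it through.** The plan gives no figure to reproduce, so the check is day arithmetic.

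**Inputs.** Window: 30 days from last dose (SAP 7.12.1). Dosing interval: 28 days in Part 3 and Schedule D, 21 in Schedule C, 14 in Schedule B (Protocol 6.1). Delay after which discontinuation is expected: more than 28 days in Part 3, more than 14 in Parts 1 and 2 (Protocol 8.4.4).

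**Formula.** Uncovered days = max(0, interval + hold − 30), counted from the last dose received.

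| Setting | Interval + hold | Uncovered |
|---|---|---|
| Part 3, Q4W, 28-day hold | 28 + 28 = 56 | 26 (days 31–56) |
| Parts 1 and 2, Q4W, 14-day hold | 28 + 14 = 42 | 12 (days 31–42) |
| Schedule C, Q3W, 14-day hold | 21 + 14 = 35 | 5 (days 31–35) |
| Schedule B, Q2W, 14-day hold | 14 + 14 = 28 | 0 |
| Q4W, no hold | 28 | 0 |

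In Part 3, holds of 2, 7, 14, 21 and 28 days leave 0, 5, 12, 19 and 26 days uncovered. At the full hold, 26/28 = 93% of the hold lies outside the window. Because of the investigator exception, 26 days is not a ceiling.

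**Which events are affected.** The SAP rule goes by when the event occurs, not by when treatment ends. Toxicity that causes a hold is normally present by the due date, about day 28, and is inside. A new event in the first two days of a Part 3 hold is also inside. What is lost is a new event with onset after day 30 in a patient who is never redosed.

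**Reconciliation.** Take a related bleed that starts on day 40, with death on day 41 and no further dose:
- on-study deaths in the overall summary: counted;
- death listing and serious AE listing: shown;
- Grade 5, drug-related serious and haemorrhage SMQ tables: absent.

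The death count and the Grade 5 tables in the same report would not agree.

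**Possible number of events.** The documents give neither the share of patients who stop after a full hold nor the event risk during one. As an illustration only, assume 2% to 20% of 118 patients per arm stop after a full 28-day hold, with a 10% to 20% chance of a Grade ≥3 event per 28 days, spread evenly:
- low: 118 × 0.02 × 0.10 × 26/28 = 0.2 events per arm;
- high: 118 × 0.20 × 0.20 × 26/28 = 4.4 events per arm.

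Protocol 4.6.2 says toxicities in the earlier parts rarely led to discontinuation, which favours the lower end. If rarely means 2% to 5% (also an assumption), the upper figure becomes 118 × 0.05 × 0.20 × 26/28 = 1.1.

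**The case against.** The strongest defence is that the SAP window matches the protocol's own AE collection period, that the worst outcomes are captured elsewhere, and that a fixed window treats patients alike. Much of this stands. Late related deaths are in the overall summary, and deaths and serious AEs are listed. The Bayesian death monitoring states no 30-day limit. Laboratory shift tables use post-baseline values with no stated 30-day limit, so prolonged cytopenia is still visible. In the dexamethasone cohort, weekly dexamethasone may continue during a hold (Protocol 8.4.2), which moves the last dose of any study treatment forward.

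The defence does not explain why a related death on day 41 is on-study while the event that caused it is missing from the Grade 5 table. Nor do listings replace tables by dose.

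A reader might infer more than the documents support:
- *The events that end treatment are the ones removed.* Not in general: the toxicity behind the hold starts by about day 28 and remains, including in the discontinuation table when recorded as the reason.
- *Affected events vanish from every output.* Related deaths and serious AEs do not.
- *The EOT allowance of 30 (+10) days adds a further 10 days.* On Q4W, days 31 to 40 already lie inside days 31–56 or 31–42, and visit timing does not alter onset dates.
- *The comparison of doses is biased.* More loss at 240 mg is conceivable, but nothing in the documents shows it, and no formal comparison of the arms is planned.

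**Conclusion.** The point holds in a limited form. In patients who never resume after a hold, new events with onset on days 31–56 after the last dose in Part 3 (days 31–42 on Q4W in Parts 1 and 2) are excluded from the serious, Grade 5, discontinuation and haemorrhage SMQ tables, although the same event would count after redosing. The day counts follow directly from the documents and assume a hold running to the limit in Protocol 8.4.4. The number of events cannot be derived; the illustrative range of 0.2 to 4.4 per arm rests entirely on assumed rates and should be read as below 1 to a few. The firmest part is the mismatch between the on-study death definition and the Grade 5, drug-related and haemorrhage tables. It should be corrected, but it does not put the safety conclusions as a whole in doubt.

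**What to change.** In SAP 7.12.1, extend the treatment-emergent definition to include any study-drug-related SAE or related Grade 5 event with onset more than 30 days after the last dose. The drug-related, serious, Grade 5 and haemorrhage SMQ tables would then reconcile with the on-study death definition.

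The cost is one definition and the matching programming. Protocol 10.3 already requires these events to be reported. In Part 3 they enter through the SAE eCRF. In Parts 1 and 2 they come on faxed SAE forms (Protocol 10.2), so check that they reach the analysis database. The downside is small: a few events further from the last dose are counted and rates rise slightly. Late events that are non-serious or judged unrelated stay out.

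Extending the window for all AEs to the discontinuation decision or the EOT visit is optional, for example as a supportive table. It would also need a change to Protocol 10.3, and follow-up would then vary with hold length, so an arm with longer holds would accrue more at-risk time.

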3) An incomplete recovery from treatment-related toxicity causing a >2 -week delay in the next scheduled infusion before the initiation of Cycle 2 (or next cycle if after cycle 1) will be considered a DLT.	Any TEAEs with AEREL="RELATED" and AEACN="DOSE DELAYED" and the next dose was delayed for >14 days

Assumptions:

- 1) Hematologic AEs include the following PTs:

Hematology collection from protocol	Preferred term
Hematocrit	“Anaemia” “Hemolysis”
Hemoglobin	“Anaemia” “Hemolysis”
Leukocytes with differential	“Leukopenia” “White blood cell count decreased”
Neutrophils (ANC)	“Neutropenia” “Neutrophil count decreased” “Febrile neutropenia”
Platelet (count)	“Thrombocytopenia” “Platelet count decreased”
Lymphocytes	“Lymphopenia” “Lymphocyte count decreased”

Note: PTs may change with coding updates.

- 2) Only include TEAEs which are related to study drug.
- 3) Duration is calculated in days, not hours e.g. 48 hours = 2 days (This would check the day of AE and the next day).
- 4) For 'Clinically significant bleeding', this is included in the non-hematologic AE part. Considering 'clinically significant' as Grade 3 or higher. No need to check for the thrombocytopenia, that is checked via the laboratory data.

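### SAP 7.12.1 pools four blood-count terms with their clinical terms but leaves out lymphocytes, so lymphopenia may be split over two rows of the adverse event tables

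*SAP*

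**What the plan says.** SAP 7.12.1 sets the level of tabulation: "Treatment-emergent AEs will be summarized by MedDRA system organ class (SOC), and preferred term". It then gives one exception, limited to the summary tables: "the following hematologic abnormalities coded to MedDRA preferred terms in the Investigations SOC will be pooled with the appropriate clinical terms". Those clinical terms belong to the Blood and lymphatic system disorders class. The mapping table under that sentence has four rows:

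- "Neutrophil count decreased" goes to Neutropenia
- "Platelet count decreased" goes to Thrombocytopenia
- "Hemoglobin decreased" goes to Anemia
- "White blood cell count decreased" goes to Leukopenia

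There is no lymphocyte row. The same section counts a patient once within each class and once within each preferred term. It presents the most common events (at least 10% of all patients) by preferred term alone.

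Appendix C of the SAP, in the first assumption of the algorithm for DLT-like events, lists the hematologic preferred terms for each blood parameter. For lymphocytes it gives Lymphopenia and "Lymphocyte count decreased".

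SAP 7.12.2 separately names lymphocyte count as an analysed laboratory parameter, with change from baseline, CTCAE grading where available, and shift tables.

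**The concern.** The purpose of the pooling rule is that a cytopenia should not be divided by whether it was coded as a clinical diagnosis or as a laboratory finding. The rule gives that protection to four cytopenias and withholds it from a fifth, for which the SAP itself expects both kinds of code. No reason is given, and no other section pools the lymphocyte terms for these tables.

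At stake is how readable one row of the safety tables is. No row would count patients with either lymphocyte term. The gap would run through every tabulation by preferred term: drug-related, Grade 3 and 4, serious, and those leading to delay, reduction or discontinuation. The 10% table is the most exposed, because it has a cut-off and does not show the organ class. Patients coded only to the laboratory term would also stay outside the Blood and lymphatic class count, unlike patients with the four pooled terms.

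**Working it through.** The documents give no lymphopenia count or coding share, so there is no figure to reproduce. The check is a comparison of the two lists, followed by a counting illustration on assumed numbers.

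**Comparison of the lists.**

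| Parameter | Clinical and count-decreased terms both in Appendix C | Pooled in SAP 7.12.1 |
|---|---|---|
| Leukocytes | yes | yes |
| Neutrophils | yes | yes |
| Platelets | yes | yes |
| Lymphocytes | yes | no |
| Hemoglobin | no (Anaemia and Hemolysis only) | yes |

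Of the four parameters for which Appendix C names both kinds of term, lymphocytes are the only one left unpooled. I take the laboratory term to sit in the Investigations class, as SAP 7.12.1 states for its four siblings.

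**Counting.** Let a be the patients with Lymphopenia, b those with Lymphocyte count decreased, and o those with both. The combined number is U = a + b − o. The two rows show a and b, and neither shows U. Each row is at most U, and is below U whenever some patient has only the other term.

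**Inputs.** N = 236, the planned Part 3 total in SAP 6.0. The cut-off is 10%: 0.10 × 236 = 23.6, so 24 patients. U, the split and the overlap are assumed.

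| Assumed U | Split and overlap | Row a | Row b | In the 10% table? |
|---|---|---|---|---|
| 30 (12.7%) | all one code | 30 (12.7%) | 0 | yes |
| 30 (12.7%) | 90/10, none | 27 (11.4%) | 3 (1.3%) | larger row only |
| 30 (12.7%) | 70/30, none | 21 (8.9%) | 9 (3.8%) | no |
| 30 (12.7%) | 50/50, none | 15 (6.4%) | 15 (6.4%) | no |
| 30 (12.7%) | 50/50, 8 with both | 19 (8.1%) | 19 (8.1%) | no |
| 46 (19.5%) | 50/50, none | 23 (9.7%) | 23 (9.7%) | no |
| 46 (19.5%) | 50/50, 12 with both | 29 (12.3%) | 29 (12.3%) | yes, both rows |
| 48 (20.3%) | 50/50, none | 24 (10.2%) | 24 (10.2%) | yes, both rows |

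**Upper limit.** Both rows miss the cut-off only if a ≤ 23 and b ≤ 23. The largest U is then 23 + 23 − 0 = 46, and 46/236 = 19.5%. Pooled, that would be one row of 19.5%. Unpooled, it is two rows of 23/236 = 9.7%, neither of which enters the table.

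**The case against.** The strongest reply is that which terms to pool is a presentation choice, and that Appendix C does not show an inconsistency. Its list identifies which terms count as hematologic for one algorithm. It also puts Anaemia beside Hemolysis and Neutropenia beside Febrile neutropenia, and SAP 7.12.1 pools neither pair. This stands in part: Appendix C shows that both lymphocyte codes are anticipated, not that they were meant to share a row.

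The second reply is that the laboratory summaries in SAP 7.12.2 do not depend on adverse event coding. Under Protocol 10.1.2 an abnormal value becomes an adverse event only if it changes treatment, needs intervention or is judged clinically significant, so these rows were never a full measure of low counts. This also stands, but it is only a partial offset. Laboratory tables carry no relatedness, seriousness or action taken, and those are what the adverse event rows add.

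A reader might infer more than the documents support:

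- That lymphopenia is in fact under-reported in this trial. No count or coding share is given, both rows remain in the full table, and the overall summary of patients with any event is unaffected.
- That Grade 4 lymphopenia is exempt from the DLT definition because it is common. Protocol 8.2 gives no reason, and the rates in Protocol 4.6.2 are for thrombocytopenia and neutropenia.
- That the Part 3 dose choice rests on these tables. Protocol 6.1 and SAP 4.4 refer to the data as a whole and do not name the per-term tables.
- That the split reflects habits at the sites. Protocol 12.0 says that events are coded with MedDRA and does not attribute the choice of term to sites.

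**Conclusion.** The omission is confirmed, and nothing else in the documents repairs it for the adverse event tables. Its effect is conditional: it needs both codes to be used and some patients to carry only one of them. The range runs from no effect to a combined incidence of just under 20% missing from the 10% table. That upper end assumes the cut-off is applied to all 236 planned Part 3 patients, with an even split and no overlap, which is the least favourable case.

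The consequence is confined to reporting. The primary endpoint and the sample size do not depend on these tables. The Part 3 safety rules watch Grade 4 or higher nonhematologic related events and treatment-related deaths, and how lymphopenia is displayed does not change those counts. The severity is minor, and the change is a free improvement.

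**What to change.** Add a fifth row to the mapping table in SAP 7.12.1, from Lymphocyte count decreased to Lymphopenia, and apply it in all summary tabulations in that section, including the 10% table. If lymphocytes were left out on purpose, say so and give the reason. The cost is one row in the SAP and one line in the mapping program, with no new data.
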